M3814 will be provided as tablet formulation of 50 mg for oral administration. Dosing schedule of the tablet formulation follows the description given for the capsule formulation above. The tablet formulation will be initially assessed in Phase Ia Arm A taking into account the available safety, tolerability and PK results from the capsule. Standard 3+3 dose escalation design criteria will apply. Comparison of single dose PK data between the tablet and the capsule will guide to define the tablet doses in Phase Ia Arm B and in the Phase Ib parts.

For subjects in Arm B receiving cisplatin:

- There will be no dose escalation of cisplatin above the protocol-specified dose. However, cisplatin dose re-escalation after an initial dose reduction, following the manufacturer's label, is permitted.
- Dose modifications for toxicity should be independently assessed prior to dose administration at each visit following institutional guidelines or [Table 13](#) in the absence of such guidelines.
- Prophylactic granulocyte-colony stimulating factor (G-CSF) may be implemented if neutropenia results in dose reduction or dose delay at prior doses, as suggested in the ASCO guidelines. Therapeutic use of hematopoietic colony-stimulating factors is permitted following ASCO guidelines.
- In the event a subject experiences neutropenia, and G-CSF is initiated, and neutropenia recovers within 48 hours after beginning treatment with G-CSF, G-CSF may be implemented in the management of neutropenia in this subject to avoid dose reductions or holding a dose.

Hemoglobin must be ≥ 10 g/dL at FD 1 and must be ≥ 9 g/dL for all subsequent doses. If hemoglobin is <9 g/dL then appropriate measures according to standard clinical practice must be taken prior to any further dose administration.

Table 13

Dose Modifications for M3814, Radiotherapy, and Cisplatin During the Trial

Toxicity	Dose Modifications		
	M3814 ^a	Radiotherapy ^b	Cisplatin (only for Arm B and in the absence of institutional guidance on cisplatin dose modifications)
Toxicities in Radiation Field Grade 4 
 Mucositis (mucosal inflammation) Radiation dermatitis 	Temporarily interrupt treatment. Resume treatment once severity resolves to Grade \leq 3.	Temporarily interrupt treatment. Resume treatment once severity resolves to Grade \leq 3.	Temporarily interrupt treatment. Resume treatment once severity resolves to Grade \leq 3.

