Systemic Toxicities 
 Febrile neutropenia Grade 3 thrombocytopenia with medically concerning bleeding Hematologic Toxicities: Any Grade \geq 4 toxicity, excluding: 
 Grade 4 neutropenia lasting for \leq 5 days and not associated with fever Isolated Grade 4 lymphocytopenia without clinical correlate 	Temporarily interrupt treatment. Resume treatment (at the same dose) once severity resolves to Grade \leq 1 or Baseline. In case of a second recurrence at the same grade, permanently discontinue IMP.	No action to be taken.	Febrile neutropenia and Grade 3 thrombocytopenia with bleeding: permanent 25% dose reduction. If on the day of scheduled treatment with cisplatin ANC is $<$ 1500/mm 3 , hold treatment until ANC \geq 1500/mm 3 , then treat at 100% dose. If on the day of scheduled treatment with cisplatin the platelet count is $<$ 75,000/mm 3 , hold treatment until platelets are $>$ 75,000/mm 3 , then treat at 100% dose.
Systemic Toxicities 
 Nonhematologic Toxicities 
 Any Grade \geq 3 toxicity, excluding: 
 Diarrhea of Grade \geq 3 (\leq 3 days duration) following adequate and optimal therapy Nausea and vomiting of Grade \geq 3 (\leq 3 days duration) with adequate and optimal therapy Fatigue or headache of Grade 3 (\leq 7 days duration) following initiation of adequate supportive care Any other single laboratory values of Grade \geq 3 out of the normal range that have no clinical significance, and that resolve to Grade \leq 2 with adequate measures within 7 days 	Temporarily interrupt treatment. Resume treatment (at the same dose) once severity resolves to Grade \leq 1 or Baseline. In case of a second recurrence at the same grade, permanently discontinue IMP. In case of Grade \geq 3 liver enzyme values, the subject must be monitored at least every 4 days until recovery to Grade \leq 2.	No action to be taken.	Institutional guidelines.

- Evidence of study treatment-related hepatocellular injury for more than 3 days, such as > 5-fold elevations above the ULN of ALT or AST (CTCAE Grade 3 or 4) with or without elevation of serum total bilirubin to > 2 x ULN, without initial findings of cholestasis (elevated serum a kaline phosphatase) or other apparent clinical causality.

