7.4.1.5 Dose Limiting Toxicities

A DLT is defined as any Grade ≥ 3 nonhematologic AE or any Grade ≥ 4 hematologic AE (according to NCI-CTCAE version 4.03) that is related to any of the study treatments and occurs during the DLT period of 5 weeks (Phase Ia, Arm A) or 12 weeks (Phase Ia, Arm B and Phase Ib, first 3 subjects in the expansion cohort of Arm A [NSCLC]) after the first dose of M3814.

A DLT must be confirmed by the SMC.

In addition, the following are considered DLTs:

1. Grade 3 thrombocytopenia with medically concerning bleeding

2. Febrile neutropenia
3. Any toxicity or study treatment-related TEAE that, in the opinion of the SMC, is of potential clinical significance such that further dose escalation would expose subjects to unacceptable risk
4. Any toxicity related to study treatments that causes the subject to receive less than 80% of the planned RT dose
5. Any toxicity related to study treatments leading to an interruption of RT longer than 1 week in Arm B
6. Evidence of study treatment-related hepatocellular injury for more than 3 days, such as > 5 -fold elevations above the ULN of ALT or AST (CTCAE Grade 3 or 4) with or without elevation of serum total bilirubin to $> 2 \times$ ULN, without initial findings of cholestasis (elevated serum alkaline phosphatase) or other apparent clinical causality.

The following study treatment-related AEs are exceptions to the above mentioned DLT definition and are **not** considered to be DLTs:

1. Mucositis (mucosal inflammation), including oral mucositis (stomatitis) of Grade ≥ 3 lasting for ≤ 4 weeks after completion of the study treatments
2. Stomatitis associated toxicities (e.g., swallowing dysfunction [odynophagia, dysphagia], decreased appetite or weight loss due to difficulty or painful swallowing) of Grade ≥ 3 lasting for ≤ 4 weeks after completion of the study treatments
3. Diarrhea of Grade ≥ 3 (≤ 3 days duration) following adequate and optimal therapy
4. Nausea and vomiting of Grade ≥ 3 (≤ 3 days duration) with adequate and optimal therapy
5. Radiation dermatitis and associated toxicities of Grade ≥ 3 lasting for ≤ 4 weeks after completion of the study treatments
6. Neutropenia of Grade 4 lasting for ≤ 5 days and not associated with fever
7. Isolated Grade 4 lymphocytopenia without clinical correlate
8. Fatigue or headache of Grade 3 (≤ 7 days duration) following initiation of adequate supportive care

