9. Any other single laboratory values of Grade ≥ 3 out of the normal range that have no clinical significance, and that resolve to Grade 2 or less with adequate measures within 7 days.

The duration of feeding tube (FT) use (nasogastric tube, percutaneous endoscopic gastrostomy) should not define the severity of the toxicity (e.g., severe swallowing dysfunction, nausea, vomiting). A careful evaluation of the subject's symptoms by the Investigator at each visit is required in order to identify subjects who are FT dependent (e.g., subjects who refuse/avoid swallowing, etc).

- In the event of severe swallowing dysfunction (Grade ≥ 3 dysphagia or odynophagia) that requires FT placement and resolves to Grade ≤ 2 prior to the end of 4 weeks after completing study treatments, if the FT is still in place for other reasons then dysphagia or odynophagia will not be considered a DLT.
- In the event of Grade 3 nausea or Grade ≥ 3 vomiting that requires FT placement and resolves to Grade ≤ 2 within 3 days, if the FT is still in place for other reasons then nausea or vomiting will not be considered a DLT.

The SMC may identify as a DLT, any ADR that impairs daily function, or abnormality occurring in subjects treated with M3814 at any time during the trial including in-field late radiation toxicities.

Subjects who discontinue treatment with M3814 because of a DLT should not be re-exposed to the trial drug but ongoing RT can continue.

Subjects who do not complete the DLT observation period for reasons other than a DLT will be replaced.

7.4.1.6 Safety Reporting to Health Authorities, Independent Ethics Committees/ Institutional Review Boards and Investigators

The Sponsor/designee will send appropriate safety notifications to Health Authorities in accordance with applicable laws and regulations.

The Investigator must comply with any applicable site-specific requirements related to the reporting of SAEs (particularly deaths) involving trial subjects to the IEC/IRB that approved the trial.

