15.2.2 Adverse Events Leading to Treatment Discontinuation

Population: SAF analysis set

An overview table of adverse events leading to discontinuation or dose reduction will be provided by dose level and overall by summarizing the number and percentage of patients with any:

- TEAE leading to temporary discontinuation of at least one trial treatment, all trial treatments, M3814 (regardless of other trial treatments status), RT (regardless of other trial treatments status), Cisplatin (regardless of other trial treatments status) (corresponding to AEs with action taken = “Drug interrupted” for MSC2490484A or Cisplatin respectively and “Dose skipped” for Radiotherapy)
- TEAE leading to permanent discontinuation of at least one trial treatment, all trial treatments, M3814 (regardless of other trial treatments status), RT (regardless of other trial treatments status), Cisplatin (regardless of other trial treatments status) (corresponding to AEs with action taken = “Drug withdrawn” for M3814, Radiotherapy or Cisplatin respectively)
- TEAE leading to dose time delayed of RT (corresponding to AEs with action taken = “Dose time delayed”)

The following frequency tables will be produced for each dose level and overall, by SOC and PT in alphabetical order:

- TEAEs leading to temporary discontinuation of at least one trial treatment
- TEAEs leading to temporary discontinuation of all trial treatments
- TEAEs leading to temporary discontinuation of M3814 (regardless of other trial treatments status)
- TEAEs leading to temporary discontinuation of RT (regardless of other trial treatments status)
- TEAEs leading to temporary discontinuation of Cisplatin (regardless of other trial treatments status)
- TEAEs leading to permanent discontinuation of at least one trial treatment
- TEAEs leading to permanent discontinuation of all trial treatments
- TEAEs leading to permanent discontinuation of M3814 (regardless of other trial treatments status)
- TEAEs leading to permanent discontinuation of RT (regardless of other trial treatments status)

- TEAEs leading to permanent discontinuation of Cisplatin (regardless of other trial treatments status)
- TEAEs leading to dose time delayed of RT

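### Table 13 and the protocol text are not reconciled on cisplatin re-escalation, on M3814 after a DLT, or on stomatitis-associated toxicities

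*Protocol*

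**What the plan says.** **Cisplatin.** After febrile neutropenia or Grade 3 thrombocytopenia with bleeding, the cisplatin column of Table 13 (Protocol Section 6.3.1) sets a "permanent 25% dose reduction". The text of the same section, just above the table, permits "cisplatin dose re-escalation after an initial dose reduction" if the manufacturer's label is followed. The column heading limits the column to Arm B and to sites with no institutional guidance on modifying cisplatin.

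**M3814.** For systemic toxicities Table 13 interrupts M3814 and then says "Resume treatment (at the same dose) once severity resolves to Grade" 1 or lower, or to baseline. It adds: "In case of a second recurrence at the same grade, permanently discontinue IMP". The RT column for these rows calls for no action. Section 7.4.1.5 lists "Grade 3 thrombocytopenia with medically concerning bleeding" and febrile neutropenia among the DLTs and requires the SMC to confirm a DLT. It then states: "Subjects who discontinue treatment with M3814 because of a DLT should not be re-exposed to the trial drug but ongoing RT can continue".

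**Exemptions.** The second DLT exemption in Section 7.4.1.5 covers "Stomatitis associated toxicities (e.g., swallowing dysfunction [odynophagia, dysphagia], decreased appetite or weight loss due to difficulty or painful swallowing") of Grade 3 or higher that last no more than 4 weeks after study treatment ends.

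**Analysis.** Protocol Section 8.4 and SAP Section 8.2 admit a subject without a DLT to the DE set only if at least 80% of planned M3814 and RT was received and the DLT period was completed. A subject with a DLT is included whatever dose was received.

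**The concern.** Section 6.3.1 presents Table 13 as the formal criteria for dose modification, so sites will dose from it. Where it meets the DLT section or the surrounding text, the reader finds two incompatible instructions (cisplatin), two instructions whose boundary is not drawn (M3814), or no clear instruction (stomatitis-associated toxicities).

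Two things are at stake. The first is conduct and safety: whether a subject receives M3814 again after a DLT may depend on which section the site consults. The second is interpretation. Delivered exposure within a dose level would partly reflect how sites read the protocol, in the cohorts from which the RP2D is set. The third point also reaches the primary endpoint, because the amount of M3814 received decides whether a subject without a DLT counts in the DLT analysis.

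**Working it through.** The plan gives no figure to reproduce. The check sets the passages side by side and adds short arithmetic where received dose matters.

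**1. Cisplatin.** A reduction that is permanent cannot also be reversed, and no passage says which sentence prevails. The scope is narrow:
- Only Arm B, and only sites without institutional guidance, by the column heading.
- On the 100 mg/m² schedule, doses fall on FD 1 and FD 31 only (Section 6.3.1.1). A reduction first applied at FD 31 leaves no later dose to re-escalate. In practice the conflict arises on the weekly 40 mg/m² schedule.

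**2. M3814 after a DLT.**
- *Overlap.* Febrile neutropenia and Grade 3 thrombocytopenia with bleeding are named in both places. The general thresholds also match (Grade 4 or higher hematologic, Grade 3 or higher nonhematologic). The event is a DLT if it is treatment-related, falls in the DLT period and is confirmed by the SMC; Table 13 has none of these conditions. The hepatocellular injury bullet is left out, because its place in the table cannot be confirmed from the extracted text.
- *Boundary.* The bar on re-exposure applies to subjects who discontinue because of a DLT. Section 7.4.1.5 does not say that a DLT requires discontinuation. The mandatory withdrawal list in Section 5.5.1 does not name a DLT.
- *Terms.* Section 6.3.1 separates interrupting from stopping. Table 13, however, adds the word permanently when it means a final stop. SAP Section 15.2.2 has the category "TEAE leading to temporary discontinuation of at least one trial treatment", mapped to the recorded action of drug interrupted. The bare verb in Section 7.4.1.5 is therefore not decisive.
- *Timing.* The cut-off for SMC dose-escalation assessments is the end of the DLT period of the cohort's last subject (Section 8.5.1). That is 5 weeks against about 2 weeks of dosing in Arm A, and 12 against about 7 in Arm B. The documents do not say when an individual DLT is confirmed, or what the site does meanwhile.
- *Size, under assumptions.* Take Arm B with 35 planned doses, an event on FD k after that day's dose, 5 fraction days to resolution, and RT continuing. Doses after restart = 35 − k − 5.
  - k = 5: 25 doses
  - k = 15: 15 doses
  - k = 25: 5 doses

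  A site that treats the event as discontinuation gives 0 in each case.

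**3. Stomatitis-associated toxicities.** The nine DLT exemptions compare with Table 13 as follows:

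| Treatment in Table 13 | Exemptions | Count |
|---|---|---|
| Repeated as an exclusion | diarrhea; nausea and vomiting; short Grade 4 neutropenia; isolated lymphocytopenia; fatigue or headache; single laboratory values | 6 |
| Handled by the Grade 4 in-field row | mucositis; radiation dermatitis | 2 |
| In no row or exclusion | stomatitis-associated toxicities | 1 |

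If the Grade 3 or higher nonhematologic row governs them, M3814 is withheld until Grade 1 or lower, or baseline, while RT continues. The 80% criterion then works out as:
- Arm B, 35 planned: 0.80 × 35 = 28 doses needed. Missing 8 gives 27/35 = 77.1%.
- Arm B, 33 planned: 0.80 × 33 = 26.4, so 27 needed. Missing 7 gives 26/33 = 78.8%.
- Arm A, 10 planned: 8 needed. Missing 3 gives 7/10 = 70%.

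At five fractions a week, 8 missed doses is a hold of 8/5 = 1.6 weeks. An exempt event is not a DLT under the standard definition, so a subject held for it with no other DLT would leave the DE set because of toxicity.

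**The case against.** The strongest reply is that most of this is not contradiction.

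On M3814, a reader might infer that Section 7.4.1.5 forbids any further dose after a DLT and that Table 13 therefore contradicts it. The documents do not support that. The bar is conditional on discontinuation, Section 5.5.1 leaves discontinuation for an adverse event to the investigator or subject, and a consistent reading exists: interrupted subjects may resume, discontinued subjects may not restart. The SAP label carries limited weight, since it needs the qualifier temporary and does not direct sites. This stands, and reduces the point to an ambiguity. It does not remove it, because no passage says which of the two a DLT triggers or what holds while confirmation is pending.

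On the exemptions, a reader might infer that the two lists should be identical. They need not be: one governs dose escalation and the other an individual's dosing, so an exempt event can still justify interruption. It is also uncertain whether in-field dysphagia belongs in a row headed as systemic, and Section 6.6.5 refers RT and M3814 toxicities to local guidelines. This too stands. What remains is that no row is named, although Section 3.6 lists these toxicities among the significant acute effects of CRT.

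On cisplatin, the permanent reduction could be read as a specific exception to a general permission. That is plausible, but the protocol does not say so.

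Finally, the SAP already lists each administration, relative dose intensity, a DLT flag and action taken (Sections 13 and 15.2.1), so re-exposure can be traced. That is correct, and subjects with a DLT stay in the DE set regardless of dose. The M3814 ambiguity therefore does not alter who counts as having a DLT in the primary analysis.

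**Conclusion.** The point holds as one direct conflict, one ambiguity and one gap.

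- **Cisplatin:** a direct conflict, limited to Arm B without institutional guidance and in practice to weekly dosing.
- **M3814 after a DLT:** an unresolved ambiguity. It mainly concerns Phase Ia and the first 3 Phase Ib NSCLC subjects, because the DLT window applies to them; the SMC may also identify a DLT at any time. In the assumed Arm B example the two readings differ by 5 to 25 doses of 35.
- **Stomatitis-associated toxicities:** a gap that can reach the primary analysis through the 80% criterion. This depends on the nonhematologic row being the one applied, on the subject having no other DLT, and on the SMC not using its discretion to classify the event as a DLT.

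The documents give no frequency for any of these events, so the number of subjects affected cannot be estimated. They show inconsistent instructions with safety relevance, not a demonstrated safety problem, and they do not change the DLT definition or any stated sample size.

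**What to change.** Reconcile the passages in one protocol amendment:

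1. State which cisplatin sentence prevails after febrile neutropenia or thrombocytopenia with bleeding.
2. State in both Table 13 and Section 7.4.1.5 whether a suspected DLT, and an SMC-confirmed DLT, leads to interruption or to a permanent stop of M3814, and what applies while confirmation is pending. Use those two terms consistently in place of the unqualified verb.
3. Name the Table 13 row, or an exclusion, that governs stomatitis-associated toxicities. The two lists can stay different if the difference is deliberate and stated.

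Which clinical rule applies in each case is for the sponsor and the SMC. The cost is protocol wording. A flag in the SAP exposure listing for M3814 given after a DLT would be convenient but is optional, because the existing listings already hold the information.

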7.4.1.7 Monitoring of Subjects with Adverse Events

Adverse events are recorded and assessed continuously throughout the trial (see Section 7.4.1.3) and are assessed for final outcome at the PTD 365 visit. All SAEs ongoing at the EOT visit must be monitored and followed up by the Investigator until stabilization or until the outcome is known, unless the subject is documented as "lost to follow-up". Reasonable attempts to obtain this information must be made and documented. It is also the responsibility of the Investigator to ensure that any necessary additional therapeutic measures and follow-up procedures are performed.

7.4.2 Pregnancy and In Utero Drug Exposure

Only pregnancies considered by the Investigator to be related to trial treatment (e.g., resulting from a drug interaction with a contraceptive medication) are considered to be AEs. However, all pregnancies with an estimated conception date during the period defined in Section 7.4.1.3 must be recorded by convention in the SAE page/section of the eCRF. The same rule applies to pregnancies in female subjects and to pregnancies in female partners of male subjects. The Investigator must notify the Sponsor/designee in an expedited manner of any pregnancy using the Pregnancy Report Form, which must be transmitted according to the same process as described for SAE reporting in Section 7.4.1.4.

Investigators must actively follow up, document and report on the outcome of all these pregnancies, even if the subjects are withdrawn from the trial.

The Investigator must notify the Sponsor/designee of these outcomes using the Pregnancy Report Form. If an abnormal outcome occurs, the SAE Report Form will be used if the subject sustains an event and the Parent-Child/Fetus AE Report Form if the child/fetus sustains an event.

Any abnormal outcome must be reported in an expedited manner as described in Section 7.4.1.4, while normal outcomes must be reported within 45 days after delivery.

In the event of a pregnancy in a subject occurring during the course of the trial, the subject must be discontinued from trial medication immediately. The Sponsor/designee must be notified without delay and the subject must be followed as mentioned above.

7.4.3 Clinical Laboratory Assessments

It is essential that the Sponsor or designee be provided with a list of laboratory normal ranges before shipment of trial drug. Any change in laboratory normal ranges during the trial will additionally be forwarded to the Sponsor or designee.

Results must be available prior to the first dose of IMP. The report of the results must be retained as part of the subject's medical record or source documents.

Blood and urine samples will be collected for the following clinical laboratory tests, following the timing noted in the Schedules of Assessments (Table 1, Table 2, Table 3, Table 4, Table 5, Table 6 and Table 7 for Phase Ia [Arm A capsule cohort], Phase Ia [Arm A tablet cohort], Phase Ib – first 3 subjects [Arm A, NSCLC cohort], Phase Ib [Arm A, NSCLC cohort], Phase Ia [Arm B, SCCHN cohort], Phase Ib [Arm B, SCCHN cohort] and ancillary cPoP parts, respectively). All samples should be clearly identified. Urinalysis (sediment and protein content) will also be performed at specified time points.

Table 15 Required Laboratory Safety Tests

Serum Chemistry	Hematology
Albumin	White blood cells and differential count
Alkaline phosphatase	Hemoglobin
Alanine aminotransferase	Hematocrit
Aspartate aminotransferase	Red blood cells
Blood urea nitrogen	Mean corpuscular volume
Calcium	Mean corpuscular hemoglobin
Creatine phosphokinase	Mean corpuscular hemoglobin concentration
Creatinine	Reticulocytes
	Platelet count
Gamma glutamyltransferase	Absolute lymphocyte count
Glucose	Absolute neutrophil count
Lactate dehydrogenase	
Magnesium	Coagulation
Phosphorous	International normalized ratio
Potassium	Activated partial thromboplastin time
Sodium	
Total bilirubin	Infection screen
Total protein	Hepatitis B
Uric acid	Hepatitis C
β-human chorionic gonadotropin in female subjects (if applicable)	Human immunodeficiency virus (according to local practice and local regulatory guidance)

For women of childbearing potential, pregnancy testing (serum β-HCG) will be performed during the Screening Period and at the visits specified in the Schedule of Assessments. Subjects after menopause (age-related amenorrhea \geq 12 consecutive months) or subjects who have undergone hysterectomy or bilateral oophorectomy are exempt from pregnancy testing.

Details on the blood volume to be drawn from each subject during the trial are presented in a separate laboratory document.

For the Phase Ia and Ib parts, including the blood volume drawn for research purposes (PK, PD markers, and PGx) and safety assessments, the total volume of blood drawn from each subject during the Screening Period (including predose) will be approximately 61 mL. During the treatment period, DLT period and Short-term Safety Follow-up (excluding predose), the total

volume of blood drawn from each subject will be approximately 138 mL (Phase Ia, Arm A), 186 mL (first 3 subjects in Phase Ib, Arm A expansion cohort [NSCLC]), 172 mL (Phase Ib, Arm A expansion cohort [NSCLC]), 210 mL (Phase Ia, Arm B) and 184 mL (Phase Ib, Arm B expansion cohort [SCCHN]). The total volume of blood drawn from each subject in the ancillary cPoP part of the trial, including blood sampling for markers, is approximately 73 mL.

